2.4.3 Extent of investigational medicinal product exposure and compliance

The extent of study treatment exposure will be assessed and summarized on the all-treated population.

2.4.3.1 Extent of investigational medicinal product exposure

The overall extent of exposure will be assessed for each patient as:

- Actual number of weeks on-treatment (duration of treatment) defined as (date of last cycle first infusion – date of first cycle first infusion + 21)/7;
- Total number of cycles started (K);
- Total number of infusions started

Overall study treatment exposure will be summarized by the total number of infusions started, the total number of cycles started, the total number of infusions received by patient, the total number of cycles received by patient and the treatment duration

Following information will also be summarized:

- Cumulative dose (mg/m^2): the cumulative dose at cycle k is the sum of all doses from cycle 1 to and including cycle k, where k is based on investigator's report.

$$\text{Cumulative Dose} = \sum_{k=1}^K \text{Actual Dose in Cycle [k]}$$

- Actual dose intensity ($\text{mg}/\text{m}^2/\text{week}$):

$$\text{ADI} = \frac{\text{Cumulative dose (mg/m}^2\text{)}}{\text{Actual no. of weeks on treatment}}$$

- Planned dose intensity ($\text{mg}/\text{m}^2/\text{week}$):

$$\text{PDI} = \frac{\text{Total Planned Dose (mg/m}^2\text{)}}{\text{Planned no. of weeks on treatment}}$$

The total planned dose will be calculated by the sum of the theoretical planned dose (i.e., the planned dose as per protocol) at each cycle:

$$\text{Total Planned Dose} = \sum_{k=1}^K \text{Planned Dose Cycle [k]}$$

Where K=total number of treatment cycles received by the patient

The planned number of weeks on treatment is defined as 3*K.

As per protocol, the planned dose at each infusion at Day 1 and Day 8 is 90 mg/m² or 120 mg/m² in each cycle in the Part 1 and the selected dose in the Part 2.

- The relative dose intensity (RDI) is defined as

$$\text{Relative Dose Intensity} = \frac{\text{Actual Dose Intensity}}{\text{Planned Dose Intensity}}$$

Summary statistics will be provided for cumulative dose, actual dose intensity and relative dose intensity.

As per protocol, for patients with a BSA >2.0 m², a BSA equals to 2.0 m² will be used for the calculation of the dose in mg/m².

Dose modifications:

Dose reduction: dose reduction will be derived using the definition provided in [Table 2](#) compared to the previous dose. For the second and subsequent infusions, a dose is deemed to have been reduced if the dose level a patient received differs from the previous actual dose level. If a dose is omitted at Day 8, then the dose reduction will be derived from the dose received at Day 1 from the previous cycle. The first infusion will not be counted for a dose reduction.

Table 2 – SAR566658 actual dose level definition (at each infusion)

Actual dose level (mg/m ²)	Actual dose administered (mg/m ²)
Upper dose	135 ≤ Dose
120	105 ≤ Dose < 135
90	83 ≤ Dose < 105
75	68 ≤ Dose < 83
60	52 ≤ Dose < 68
Lower dose	0 < Dose < 52
No dose administered	0

Dose omission: at a given infusion, dose omission will be considered if no drug is administered (dose=0 mg/m²). Number of dose omissions within a cycle will be equal to the difference between expected number of infusions and number infusions actually received.

Infusion delayed: a dose at Day 22 (Day 1 of next cycle) is deemed to have been delayed if the study treatment is ≥4 days beyond the theoretical day of treatment. The first dose will not be counted for dose delay.

Dose interruption: dose interruption will be considered if the study treatment infusion is temporarily stopped during the infusion.

Number of patients (%) and number of cycles (%) with at least one SAR566658 dose modification (including dose reduction, dose omission, cycle delayed) and dose interruption, overall and by type, will be provided.

Number of SAR566658 infusions (%) with a dose modification, overall and by type, will be also provided.

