8.2.3.1 Dose modification

Dose can be reduced for SAR566658 when necessary, as described in the following sections. The dose, which has been reduced due to an AE, must not be re-escalated. Up to a maximum of 2 dose

reductions will be allowed per patient. If a third dose reduction is required per the modifications below, the patient should discontinue study treatment. Dose levels for each arm in case of dose reduction are described in [Table 2](#) below.

The patient may have the Day 8 dose omitted if an AE occurs and they have not recovered on the theoretical day of infusion. The patient will receive the next cycle after recovery from the AE, as described.

Table 2 - Dose reduction levels

	Initial dose (mg/m ²)		Dose reduction 1 (mg/m ²)		Dose reduction 2 (mg/m ²)
SAR566658	90	→	75	→	60
SAR566658	120	→	90	→	75

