10.4.1.3 Adverse event of special interest

An adverse event of special interest (AESI) is an AE (serious or nonserious) of scientific and medical concern specific to the Sponsor’s product or program, for which ongoing monitoring and immediate notification by the Investigator to the Sponsor is required. Such events may require further investigation in order to characterize and understand them. Adverse events of special interest may be added, modified or removed during a study by protocol amendment.

- Pregnancy of a female subject entered in a study as well as pregnancy occurring in a female partner of a male subject entered in a study with IMP/noninvestigational medicinal product (NIMP):

Pregnancy occurring in a female patient entered in the clinical trial or in a female partner of a male patient entered in the clinical trial. It will be qualified as an SAE only if it fulfills 1 of the seriousness criteria (see [Section 10.4.1.2](#)).

- In the event of pregnancy in a female participant, IMP should be discontinued.
- Follow-up of the pregnancy in a female participant or in a female partner of a male participant is mandatory until the outcome has been determined (see [Appendix C](#)).
- Symptomatic overdose (serious or nonserious) with IMP/NIMP:
 - An overdose (accidental or intentional) with the IMP/NIMP is an event suspected by the Investigator or spontaneously notified by the patient and defined as at least twice the intended dose within the intended therapeutic interval, adjusted according to the tested drug,
 - Infusion: increase of at least 30% of the highest planned dose (eg, 120 mg/m²) to be administered in the specified duration or if the dose is administered in less than half the recommended duration of administration,
 - Injectable administration: at least twice the dose during the planned intervals.

Of note, asymptomatic overdose has to be reported as a standard AE.

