11.4.2.1 Extent of investigational medicinal product exposure

The following variables will be calculated and summarized with descriptive statistics to describe exposure to SAR566658:

- Number of cycles started and duration of exposure in weeks, defined as $([\text{First day of last cycle} - \text{first day of first cycle} + 21 \text{ days}]/7)$.
- Cumulative dose (in mg/m^2), defined as the sum of all doses administered from first to last dose.
- Actual dose intensity, defined as the cumulative dose divided by the number of weeks on study.
- Relative dose intensity (in %), defined as the ratio of the actual dose intensity to the planned dose intensity. The relative dose intensity is an indicator of the feasibility of the chosen schedule of administration.
- Cycle delays: a dose at Day 22 (Day 1 of next cycle) is deemed to have been delayed if the study treatment is ≥ 4 days beyond the theoretical day of treatment.

- Dose reduction: for the second and subsequent infusions, a dose is deemed to have been reduced if the dose level a patient receives differs from the previous actual dose level. The first infusion will not be counted for a reduction.
- Infusion omission (Day 8): at a given infusion, dose omission will be considered if no drug is administered (dose=0 mg/m²). Number of dose omissions within a cycle will be equal to the difference between expected number of infusions and number infusions actually received.
- Dose interruption: administration of SAR566658 infusion is temporarily stopped during the infusion.

Dose information variables will be assessed for each patient and summarized descriptively (N, mean, standard deviation, median, minimum, and maximum). Analyses will be performed based on the number of patients and on the number of cycles.

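### The dose-reduction rule has no direction, so an upward change of dose level after the first infusion is counted as a reduction in the exposure tables

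*SAP*

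**What the plan says.** SAP 2.4.3.1 derives a dose reduction by placing each infusion in one of the dose levels of its Table 2, "compared to the previous dose". The rule is that "a dose is deemed to have been reduced if the dose level a patient received differs from the previous actual dose level". Protocol 11.4.2.1 agrees: "a dose is deemed to have been reduced if the dose level a patient receives differs from the previous actual dose level".

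Two qualifiers follow in the SAP. One is an exemption: "The first infusion will not be counted for a dose reduction". The other covers an omitted Day 8 dose: "then the dose reduction will be derived from the dose received at Day 1 from the previous cycle". The second changes what the dose is compared with. Neither supplies a direction.

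Table 2 has six non-zero levels: a lower level (above 0 and below 52 mg/m²), 60 (52 to below 68), 75 (68 to below 83), 90 (83 to below 105), 120 (105 to below 135) and an upper level (135 or more). SAP 2.4.3.1 then tabulates patients and cycles with at least one dose modification, and infusions with one, overall and by type. It has no category for an increase in dose level.

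**The concern.** The sentence is a derivation rule, and a programmer who follows it will code 'not equal to the previous level'. Any rise between Table 2 levels after the first infusion then enters the tables as a reduction. This covers the return to full dose after an incomplete infusion, a re-escalation made in breach of the protocol, and a dose above plan. A dose above plan would thus be reported as its opposite.

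What is at stake is the accuracy of the exposure tables, which are shown by dose level in Part 1 with 14 patients per arm. At that size one misclassified patient is visible in the percentage. Two programmers could also reach different counts, one following the word 'reduced' and the other the word 'differs'.

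**Working it through.** The plan states no figure that depends on this rule, so there is nothing to reproduce. The check applies the rule to the Table 2 levels.

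**Inputs.** The level boundaries are those of SAP Table 2. The reduction steps are those of protocol Table 2 (120 to 90 to 75, and 90 to 75 to 60). For infusions, protocol 10.4.1.3 sets the overdose threshold at an "increase of at least 30% of the highest planned dose", that is 1.30 × 120 = 156 mg/m², which falls in the upper level. Part 1 has 14 patients per arm.

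**Transitions.** Six non-zero levels give 6 × 5 = 30 ordered pairs of different levels. Half, 15, are increases. The literal rule counts all 30 as reductions; a rule requiring a lower level counts 15.

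**Sequences.** Each row shows consecutive infusions in mg/m². The first infusion is never counted. Rule A is 'differs from the previous level'. Rule B is 'lower than the previous level'. Rule C is B without returns from an above-plan dose to the planned level.

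| Infusions | Table 2 levels | A | B | C |
|---|---|---|---|---|
| 120, 40, 120 | 120, lower, 120 | 2 | 1 | 1 |
| 40, 120, 120 | lower, 120, 120 | 1 | 0 | 0 |
| 120, 120, 156 | 120, 120, upper | 1 | 0 | 0 |
| 120, 120, 156, 120 | 120, 120, upper, 120 | 2 | 1 | 0 |
| 156, 120, 120, 120 | upper, 120, 120, 120 | 1 | 1 | 0 |
| 120, 90, 120, 120 | 120, 90, 120, 120 | 2 | 1 | 1 |
| 120, 120, 40 | 120, 120, lower | 1 | 1 | 1 |
| 120, 110, 120 | 120, 120, 120 | 0 | 0 | 0 |
| 90, 104, 90 (90 arm) | 90, 90, 90 | 0 | 0 | 0 |
| 120, 120, 90, 90, 75, 75 | 120, 120, 90, 90, 75, 75 | 2 | 2 | 2 |
| 90, 90, 75, 75, 60, 60 (90 arm) | 90, 90, 75, 75, 60, 60 | 2 | 2 | 2 |

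**From infusions to the tabulated quantities.**

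- *Infusions.* Every upward change of level adds one false reduction.
- *Cycles.* With 120, 40, 120, if the 40 is Cycle 1 Day 8 and the next 120 is Cycle 2 Day 1, Cycle 2 is wrongly flagged. If the low dose and the return fall in the same cycle, the cycle count does not change.
- *Patients.* With 120, 40, 120 the patient counts once under either rule. The patient count changes only when there is no real decrease in level, as in 40, 120, 120 or 120, 120, 156. One such patient in a Part 1 arm adds 1/14 = 7.1 percentage points.

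**Why B alone is not enough.** In 156, 120, 120, 120, rules A and B both count the return to the planned dose as a reduction. Only rule C removes it.

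**The case against.** The best defence is that the heading and the verb both speak of reduction, so a decrease was plainly meant, and that compliant patients rarely move upward because "The dose, which has been reduced due to an AE, must not be re-escalated". Both points carry some weight. The intent is probably as stated, and the table above confirms that planned step-downs count the same under every rule. But the ban covers only doses reduced because of an adverse event. It does not reach a full dose given after an incomplete infusion, and it does not stop a deviation from being counted once it has happened. Intent does not settle the matter either, because the operative sentence says something else in both documents.

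A reader might infer more than the documents support, in three ways.

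- *That the rule distorts the choice between 90 and 120 mg/m².* The selection criteria in protocol 6.3 and SAP 1.1 refer to adverse events leading to dose modification, reduction or discontinuation. SAP 2.4.5.1 builds its tables of events leading to dose modification or reduction from the investigator's action taken on the adverse event page, not from the Table 2 derivation.
- *That every partial infusion is counted twice.* A partial first infusion is exempt, so only the return counts. A partial last infusion counts once. A partial dose that stays within its level does not count.
- *That interrupted infusions are over-counted.* SAP 2.4.3.1 defines interruption as a temporary stop. An infusion that is stopped, resumed and completed does not change level and is never counted as a reduction.

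**Conclusion.** The point holds as a wording error with a small reach. Read literally, both documents count any upward change of Table 2 level after the first infusion as a dose reduction. The excess falls mainly on the infusion-level counts. Cycle counts change when the rise falls in a cycle without a real reduction, and patient counts change only for patients with no real decrease, at 7.1 percentage points per patient in a Part 1 arm.

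This rests on two assumptions: that the rule is programmed as written, and, for the patient-level figure, that the patient has no genuine reduction elsewhere. For the overall figure, the patient must also have no other dose modification. The documents give no frequency for incomplete infusions or doses above plan, so the expected number of false reductions cannot be stated.

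Cumulative dose and dose intensity are computed from doses given, not from this flag. The response-rate test and the Bayesian monitoring of the predefined safety criteria do not use it either. Severity is minor.

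**What to change.** In SAP 2.4.3.1 and protocol 11.4.2.1, make three changes to the derivation:

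1. Define a reduction as a dose level lower than the previous actual dose level, in place of one that differs from it.
2. Tabulate increases in dose level as a separate category.
3. State that a return from an above-plan dose to the planned level is not a reduction.

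Leave the definition of dose interruption unchanged and do not move partial infusions into it. An infusion that is stopped and not completed is not a temporary stop, so reclassifying it would contradict the SAP's own definition.

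The cost is a few words in two documents, one extra table row and minor programming. Data collection, sample size and study conduct do not change.

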2.4.4 Analyses of efficacy endpoints

2.4.4.1 Analysis of primary efficacy endpoint(s)

Response rate will be analyzed based on all-treated population as defined in the [Section 2.3.1.1](#).

Overall Response rates will be summarized using counts (n) and percentages (%) and presented with its 2-sided 80% confidence interval using the Clopper and Pearson exact method.

At the end of the Part 2a in the overexpression cohort at the selected dose, an exact binomial test of the null hypothesis that the true response rate is 12% will be performed using a one-sided 0.1 alpha level.

Best Overall Response (BOR) (CR, PR, SD, PD, and NE) will be summarized using counts (n) and percentages by treatment group. At the end of the part1, a summary of BOR by intended dose levels and ECOG stratification factor will also be provided.

For responder patients, a listing with number of prior advanced regimen, prior treatment with anthracycline and/or taxanes (yes/no), prior treatment with eribulin (yes/no), best response to last advanced previous anti therapy, baseline CA6 IHC, baseline circulating CA6, best overall response to SAR566658, duration of response and reason for treatment discontinuation will be provided.

Exploratory analyses

At the end of the Part 2a in the overexpression cohort, ORR will be estimated (with its 80% CI) in several subgroups of patients defined in the table below. A forest plot with estimation of ORR in each subgroup will be provided, if enough patients in each stratum. Depending upon the study results, additional subgroups may be examined, and subgroups with small sample sizes may be pooled to create a larger meaningful subgroup.

Table 3 – Subgroup analyses

Prognostic factor	Description
Age	[18-65[y, [65-75[y, ≥75y
ECOG PS at baseline	0, 1
Any prior eribulin agent	Yes vs No
Mutation BRCA1	Yes vs No
Mutation BRCA2	Yes vs No
Number of organs involved	1,2 ≥3
Number of prior regimen	1,2,3
Bone metastasis only vs visceral metastasis	Yes vs No
DFS	≤24 mo vs >24mo
PD1	Classes to be defined
PDL1	Classes to be defined

Sensitivity analyses of the primary efficacy endpoint

The ORR will also be estimated on the response-evaluable population as defined in [Section 2.3.1.2](#). Depending on the results, exploratory analyses as defined in the [Table 3](#) may also be performed on the response-evaluable population.

2.4.4.2 Analyses of secondary efficacy endpoints

2.4.4.2.1 Disease Control rate

Disease control rate will be summarized using counts (n) and percentages by treatment group. Confidence intervals at 80% will be computed using the Clopper and Pearson exact method.

The DCR will also be estimated on the response-evaluable population as defined in [Section 2.3.1.2](#).

2.4.4.2.2 Duration of response

Duration of response will be analyzed in responders using the Kaplan-Meier method. Kaplan-Meier estimates and associated 80% CI will be provided.

2.4.4.2.3 Tumor shrinkage

A graphical representation of the best tumor shrinkage observed per patient (waterfall plot) will also be provided on the all-treated population.

2.4.4.2.4 Time to progression

The median TTP and its 80% confidence interval will be estimated on the all-treated population.

Kaplan-Meier estimates of the 25th, 50th, and 75th percentiles and their associated 80% CIs will be provided.

Number of patients at risk as well as the probabilities of surviving without disease progression at least 3, 6, 9, and 12 months with 80% confidence intervals will be estimated using the Kaplan-Meier method.

The number (%) of censored patients and the timing of their censoring (ie, censored at randomization, censored at last disease assessment) will be summarized. Kaplan-Meier curves will be plotted. These plots will include the number of patients at risk at key time points.

2.4.4.2.5 Progression Free Survival

PFS data will be analyzed using the Kaplan-Meier method in the all treated population:

- Kaplan-Meier estimates of the 25th, 50th, and 75th percentiles and their associated 80% CIs will be provided. The 80% confidence intervals will be constructed using a log-log transformation of the survival function and the methods of Brookmeyer and Crowley.
- Number of patients at risk as well as the probabilities of surviving without disease progression at least 3, 6, 9, and 12 months with 80% confidence intervals will be estimated using the Kaplan-Meier method.
- Kaplan-Meier curves will be plotted. These plots will include the number of patients at risk at key time points.

For patients with events, the type of event (objective disease progression or death for primary analysis and also clinical/non radiological progression for sensitivity analysis) will be summarized using counts and percentages. The type of disease progression will be presented for sensitivity analysis (objective disease progression or clinical/non radiological progression).

For patients who died without evidence of disease progression, the time from the last disease assessment to death will be summarized using number, mean, standard deviation, median, and range.

The number (%) of censored patients and the timing of their censoring (ie, censored at randomization, censored at last disease assessment) will be summarized.

2.4.4.3 Multiplicity issues

No adjustment for multiplicity linked to the selection of dose will be done.

2.4.5 Analyses of safety data

The summary of safety results will be presented by dose levels in the Part 1 and by CA6 expression level cohort in the Part 2 (mild expression and overexpression).

General common rules

All safety analyses will be performed on the all-treated population as defined in [Section 2.3.1.1](#), unless otherwise specified, using the following common rules:

- Safety data in patients who do not belong to the all-treated population (eg, treated but not randomized) will be listed separately.
- The baseline value is defined as the last available value before first study treatment infusion.
- The analysis of the safety variables will be essentially descriptive.

2.4.5.1 Analyses of adverse events

Generalities

The primary focus of adverse event reporting will be on treatment-emergent adverse events as defined in [Section 2.1.4](#). Pretreatment and post-treatment adverse events will be described separately.

If an adverse event date of onset (occurrence or becoming serious) is incomplete, an imputation algorithm will be used to classify the adverse event as pretreatment, treatment-emergent, or post-treatment. The algorithm for imputing date of onset will be conservative and will classify an adverse event as treatment emergent unless there is definitive information to determine it is pretreatment or post-treatment. Details on classification of adverse events with missing or partial onset dates are provided in [Section 2.5.4](#).

The grade will be taken into account in the summary. For patients with multiple occurrences of the same event, the maximum (worst) NCI grade is used within the same period of observation (pretreatment, treatment, post-treatment). Summaries will be provided for all grades and for grade ≥ 3 (including grade 5). Missing grades, if any, will be included in the “all grades” category. Sorting within tables ensures the same presentation for the set of all adverse events within the observation period (pretreatment, treatment-emergent and post-treatment). For that purpose, the table of all treatment-emergent adverse events presented by SOC and PT sorted by the internationally agreed SOC order and decreasing frequency of PTs within SOCs will define the presentation order for all other tables unless otherwise specified. In part 1, sorting will be based on results for the dose level 120mg/m² D1D8 Q3w and in part 2, sorting will be based on the All column including overexpression and mild expression cohorts at the selected dose.

Analysis of all treatment-emergent adverse events

The following treatment-emergent adverse event summaries will be generated for the all-treated population. Overview of treatment-emergent adverse events, summarizing number (%) of patients with any

- TEAE
- Grade ≥ 3 TEAE

- Grade 3-4 TEAE
- Grade 5 TEAE (any TEAE with a fatal outcome during the treatment period)
- Serious TEAE
- TEAE leading to permanent treatment discontinuation

In addition, an overview of Grade 5 AEs will be provided.

The following frequency distributions of AEs (incidence tables) will also be provided for the all-treated population, for all grades combined and grade ≥ 3 .

- All treatment-emergent adverse events by primary SOC, HLGT, HLT, and PT, showing number (%) of patients with at least 1 TEAE sorted by the SOC internationally agreed order. The other levels (HLGT, HLT, PT) will be presented in alphabetical order.
- All treatment-emergent adverse events by primary SOC and PT, showing the number (%) of patients with at least 1 treatment-emergent adverse event, sorted by the internationally agreed SOC order and by decreasing incidence of PTs within each SOC as previously defined. This sorting order will be applied to all other tables, unless otherwise specified.
- All related treatment-emergent adverse events by primary SOC, HLGT, HLT, and PT, showing number (%) of patients with at least 1 related TEAE sorted by the internationally agreed SOC order. The other levels (HLGT, HLT, PT) will be presented in alphabetical order.
- All related treatment-emergent adverse events by primary SOC and PT, showing the number (%) of patients with at least 1 related TEAE, sorted by the sorting order defined above.

Analysis of all treatment emergent serious adverse event(s)

All serious TEAEs will be presented by primary SOC and PT, showing the number (%) of patients with at least 1 serious TEAE, sorted by the internationally agreed SOC order and by decreasing incidence of PTs within each SOC.

All treatment-emergent serious adverse events will be presented by primary SOC, HLGT, HLT, and PT, showing the number (%) of patients with at least 1 serious treatment-emergent adverse event, sorted by the internationally agreed SOC order. The other levels (HLGT, HLT, PT) will be presented in alphabetical order.

All treatment-emergent serious adverse events regardless of relationship and related to IMP will be presented by primary SOC, HLGT, HLT, and PT, showing the number (%) of patients with at least 1 serious treatment-emergent adverse event, sorted by the internationally agreed SOC order. The other levels (HLGT, HLT, PT) will be presented in alphabetical order.

Analysis of all treatment-emergent adverse event(s) leading to treatment discontinuation

All treatment-emergent adverse events leading to permanent treatment discontinuation will be presented by primary SOC, HLGT, HLT, and PT, showing the number (%) of patients sorted by the internationally agreed SOC order. The other levels (HLGT, HLT, PT) will be presented in alphabetical order.

All TEAE leading to treatment permanent discontinuation will be presented by primary SOC and PT, showing the number (%) of patients with at least 1 TEAE leading to treatment discontinuation, sorted by the internationally agreed SOC order.

Analysis of all treatment-emergent adverse event(s) leading to dose modification

The following summary tables are based on the investigator's intent reported in the AE page ("action taken"):

- All treatment-emergent adverse events leading to dose modification (delay and/or reduction/omission), by primary SOC and PT, showing the number (%) of patients, sorted by the sorting order defined above.
- All treatment-emergent adverse events leading to dose reduction/omission, by primary SOC and PT, showing the number (%) of patients, sorted by the sorting order defined above.
- All treatment-emergent adverse events leading to dose interruption, by primary SOC and PT, showing the number (%) of patients, sorted by the sorting order defined above.
- All treatment-emergent adverse events leading to dose delay, by primary SOC and PT, showing the number (%) of patients, sorted by the sorting order defined above.

Analysis all treatment-emergent adverse events(s) with fatal outcome

All TEAEs with fatal outcome will be presented by primary SOC, HLGT, HLT and PT, showing the number (%) of patients sorted by the internationally agreed SOC order. The other levels (HLGT, HLT, PT) will be presented in alphabetical order

Analysis of adverse events of special interest

Number (%) of patients with at least one AESI cited in [Section 2.1.4](#) will be presented.

Analysis of ocular toxicities and peripheral neuropathy

For each TEAE, the number (%) of patients by worst grade, the cycle of first occurrence regardless of the grade, the cycle of first occurrence of the worst grade, the relationship to study treatment (in case of several occurrences with different relationships, if any event is related, then the relationship will be 'Related'), the action taken with the study treatment (in case multiple occurrences with different actions, the most severe action taken will be tabulated and selected according to the following order of severity: drug withdrawn, dose reduced and delayed, dose reduced/omitted, dose delayed, drug interruption, dose not changed, not applicable), the outcome

(in case of multiple occurrences with different outcomes, the most severe outcome will be tabulated and selected according to the following order of severity: fatal, not recovered or resolved, recovering or resolving, recovered or resolved with sequelae, recovered or resolved, unknown) and the number of recurrences.

Analysis of pre-treatment and post-treatment adverse events

Overview of pre-treatment adverse events, summarizing number (%) of patients with any

- Pre-treatment adverse events
- Grade ≥ 3 pre-treatment treatment adverse events
- Grade 3-4 pre-treatment adverse events
- Serious pre-treatment adverse events
- Grade 5 pre-treatment adverse events

Overview of post-treatment adverse events, summarizing number (%) of patients with any

- Post-treatment adverse events
- Grade ≥ 3 post-treatment treatment adverse events
- Grade 3-4 post-treatment treatment adverse events
- Grade 5 post-treatment adverse events (including TEAE worsening to Grade 5 during the post-treatment period)
- Serious post-treatment adverse events

All pre-treatment AEs by primary SOC and PT, showing the number (%) of patients with at least 1 pre-treatment AE, sorted by the internationally agreed SOC order and decreasing incidence of PTs within each SOC.

All post-treatment AEs by primary SOC and PT, showing the number (%) of patients with at least 1 post-treatment AE, sorted by the internationally agreed SOC order and decreasing incidence of PTs within each SOC

Some listings might also be reported if judged more relevant.

